7. PROTOCOL DEVIATIONS

Protocol deviations will be reviewed periodically over the course of the study. The review process, definition of the deviation categories, and the classification of a deviation as major or minor are detailed in the Protocol Deviation Management Plan.

Major protocol deviations will be assigned to 2 stages for the summary of major protocol deviations by stage. If a major protocol deviation happens or is identified on or after the Stage 2 randomization date or the Study Week 5 visit date for those who were not randomized into Stage 2, the major protocol deviation will be assigned to Stage 2; else it will be assigned to Stage 1.

A summary of the number and percentage of subjects with major protocol deviations by deviation category and treatment group will be provided for RAS1 (up to Study Week 5/Early termination) and RAS2 (from Study Week 5 to Study Week 10/Early termination). A listing of protocol deviations by site and subject will also be provided.

8. DEMOGRAPHICS AND OTHER BASELINE CHARACTERISTICS

Demographics and baseline characteristics will be summarized by treatment group and overall for RAS1, RAS2, SAS1, SAS2, FAS1, FAS2, PAS1, and PAS2 using descriptive statistics. Variables include age, age group (18-40 years and > 40 years), sex, race, ethnicity, height, weight, BMI, current smoker, highest education level, marital status, employment status, Montgomery Asberg Depression Rating Scale (MADRS) total score, Baseline HAMD-17 total score, Baseline HAMD-17 total score < 24 and ≥ 24 , Baseline SDS mean score, and Baseline Clinical Global Impressions-Severity Illness (CGI-S).

Race will also be categorized by White vs. Non-White. The reported age reflects a subject's age at the informed consent date. Baseline CGI-S will be summarized as both a continuous variable and a categorical variable.

Depression history will be summarized by treatment group for RAS1, RAS2, SAS1, SAS2, FAS1, FAS2, PAS1, and PAS2 using descriptive statistics. Variables include:

- Age at first onset of depression symptoms
- Age at MDD diagnosis
- Duration of the current MDE (months relative to the informed consent date)
- Number of depression episodes during the subject's lifetime
- Number of hospitalizations for depression during the subject's lifetime

Depression history as described above, date of last hospitalization (if number of hospitalizations is greater than 0), and onset date for the current episode of depression will also be presented in a data listing.

Massachusetts General Hospital Antidepressant Treatment Response Questionnaire (MGH ATRQ) examines a patient's antidepressant treatment history and determines the adequacy of treatment response. MGH ATRQ is collected at Screening visit. Drug type, generic name, took during this current episode of depression (Yes/No), dose, and took at least this dose for at least 8 weeks (Yes/No), and the amount of improvement in percentage will be listed.

9. MEDICAL HISTORY

Medical history reported terms will be coded with Medical Dictionary for Regulatory Activities (MedDRA), version 19.0 or newer. The subject incidence will be summarized for each system organ class (SOC) and preferred term by treatment group and overall for FAS1, FAS2, SAS1, and SAS2. A subject will be counted only once per SOC or per preferred term for the summary.

A listing of the SOC, preferred term, body system, verbatim for the medical history condition/event, start and stop dates (when available), and an indicator for whether or not the condition is ongoing will be provided.

10. EXTENT OF EXPOSURE AND TREATMENT COMPLIANCE

Extent of exposure and treatment compliance will be summarized as continuous variables by treatment group for SAS1 in Stage 1 (5 weeks), SAS2 in Stage 2 (5 weeks), and the subjects in SAS1 who were not randomized to the pimavanserin group in Stage 2 (10 weeks).

10.1 Exposure to Study drug

Duration of exposure to study drug will be calculated for each subject as (last dose date – first dose date + 1).

For SAS1 and SAS2, the number and percentage of subjects within each of the following exposure levels (a maximum of 5 weeks [approximately 35 days]) in terms of duration (days) of exposure will also be tabulated: ≤ 10 , 11- ≤ 20 , 21- ≤ 30 , and > 30 . For the PIM subjects vs. the placebo subjects in SAS1 who were not randomized to the pimavanserin group in Stage 2, the exposure levels will be: ≤ 20 , 21- ≤ 40 , 41- ≤ 60 , and > 60 . Kaplan-Meier curves of duration on study drug will also be presented for each treatment group.

10.2 Measurement of Treatment Compliance

Study drug dosing compliance for a specified period is defined as the total number of tablets actually taken by a subject during that period divided by the number of tablets expected to be taken during the same period multiplied by 100. The total number of tablets actually taken is calculated by the total number of tablets dispensed minus the number of tablets returned. The number of tablets expected to be taken for a specified period is calculated as (last dose date – first dose date + 1) x 2 (the planned number of tablets taken per day).

Treatment compliance will be summarized as both a continuous variable and a categorical variable. For the categorical presentation, the number and percentage of subjects within each of the following compliance levels will be tabulated: $< 40\%$, 40 - $< 60\%$, 60 - $< 80\%$, 80 - $\leq 120\%$, and $> 120\%$.

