5.1.1 Formulation, Appearance, Packaging, and Labeling

ACADIA will supply pimavanserin 17 mg strength tablets and matching placebo tablets.

Pimavanserin tartrate is a white to off-white powder. Pimavanserin tablets include the active compound (pimavanserin) and the following [REDACTED]. The drug product is formulated with standard pharmaceutical excipients at 17 mg strength (20 mg of pimavanserin tartrate). Pimavanserin treatment consists of 2 tablets once-daily for oral administration.

Placebo tablets contain all of the same excipients as pimavanserin 17 mg tablets, but do not contain any pimavanserin.

Pimavanserin and placebo used for the tablets are manufactured under current Good Manufacturing Practice compliance by [REDACTED]

During the treatment period, study drug will be supplied in Treatment Kits. Each Treatment Kit which will contain one (1) Blister Card. Each Blister Card contains 20 tablets. Each Treatment Kit contains 10 days of treatment (7 days treatment + 3 days extra).

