5.1.3 Dosing and Administration

The first dose of study drug will be administered at the clinic during the Baseline visit; study drug kits will then be dispensed to the subject to take home. On the second day, patients should take the study drug at the time that they plan to usually take it. Each daily dose consists of 2 individual tablets that should be taken together. Subjects should be instructed to take 2 tablets, orally, once each day, at approximately the same time. The tablets may be taken with or without food.

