6.5.2 Baseline (Week 0)

At Baseline, after Screening procedures are completed and reviewed (e.g., acceptable clinical laboratory tests), the subject will be evaluated for continued eligibility and if qualified, may enter the treatment phase and receive the first dose study drug. Subjects will complete the following procedures at Baseline:

- Physical examination
- Vital signs (pre-dose; sitting [at least 3 minutes] BP, pulse, respiratory rate, and temperature)
- Weight
- 12-lead ECG (single recording; before blood sampling or at least 30 minutes after blood sampling). May be repeated once in consultation with the medical monitor.
- Clinical laboratory tests
- Serum and urine pregnancy tests for women of childbearing potential
- Urine toxicity screen (done by central lab)
- PK blood draw (pre-dose) for pimavanserin, AC-279, and concomitant SSRI/SNRI concentrations
- Assessment of concomitant medications

- Assessment of AEs
- Scales listed in [Table 2](#) (MADRS, HAMD-17, CGI-S, SF-12, SDS, DAI-10, MGH-SFI, KSS, BIS-11, SIS, C-SSRS, AIMS, BARS, and SAS).
 - The C-SSRS time frame is since last visit.
- Randomization
- Dispense and administer first dose of study drug
 - Each subject will be assigned study drug according to the randomization schedule. The first dose will be administered at the clinic; study drug kits will then be dispensed to the subject to take home. It is recommended that the subject take the study drug at approximately the same time each day.

6.5.3 Week 1

Subjects will complete the following procedures:

- Vital signs (sitting [at least 3 minutes] BP, pulse, respiratory rate, and temperature)
- Weight
- 12-lead ECG (single recording; before blood sampling or at least 30 minutes after blood sampling)
- PK blood draw for pimavanserin, AC-279, and concomitant SSRI/SNRI levels
- Assessment of concomitant medications
- Assessment of AEs
- Scales listed in [Table 2](#) (HAMD-17, CGI-S and I, SDS, KSS, BIS-11, SIS, C-SSRS, AIMS, BARS, and SAS)
 - The C-SSRS time frame is since last visit
- Study drug accountability
- Dispense study drug

6.5.4 Week 2

Subjects will complete the following procedures:

- Vital signs (sitting [at least 3 minutes] BP, pulse, respiratory rate, and temperature)
- Weight
- Assessment of concomitant medications
- Assessment of AEs
- Scales listed in [Table 2](#) (HAMD-17, CGI-S and I, SDS, KSS, C-SSRS)

- The C-SSRS time frame is since last visit
- Study drug accountability
- Dispense study drug

6.5.5 Week 3

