7.4.4 Reporting of Overdose

An overdose of study drug (i.e., any amount more than the prescribed 2 tablets in a given day) must be reported on the Overdose Form within 24 hours of discovery to ACADIA or its designee (see fax numbers and email address in [Section 7.4.2](#)).

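### SAP 10.2 counts every unreturned tablet as taken, so with overfilled weekly kits a lost, untaken kit raises reported compliance instead of lowering it; the damage is to a descriptive table

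*SAP*

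**What the plan says.** SAP Section 10.2 defines compliance for a period as tablets taken over tablets expected, times 100. The numerator is stated outright: "The total number of tablets actually taken is calculated by the total number of tablets dispensed minus the number of tablets returned". The denominator is the number of days from first to last dose, inclusive, times 2, described as "the planned number of tablets taken per day". Results are summarized as a continuous variable and in five bands: below 40%, 40 to <60%, 60 to <80%, 80 to 120%, and above 120%. SAP Section 10 applies this by treatment group "for SAS1 in Stage 1 (5 weeks), SAS2 in Stage 2 (5 weeks"), and over 10 weeks for Stage 1 safety-set subjects not randomized to pimavanserin in Stage 2.

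The supply is described in the protocol. On dose, Section 5.1.3 says "Each daily dose consists of 2 individual tablets that should be taken together". On packaging, Section 5.1.1 says "Each Blister Card contains 20 tablets", with one card per kit, and "Each Treatment Kit contains 10 days of treatment (7 days treatment + 3 days extra"). In Table 2 the row "Dispense study drug" is marked at every visit from Baseline to Week 9.

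Protocol Section 5.2 tells subjects to bring back packs and leftover tablets, and asks sites to record drug dispensed, used and returned. The SAP formula uses only the first and last of these. SAP Sections 5.4 to 5.8 give fallback rules for missing dates and for missing severity and causality of adverse events. Neither document gives one for drug that is not returned.

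**The concern.** Dispensed minus returned measures intake only when everything not swallowed comes back. A kit that is lost, discarded or left at home breaks that condition, and the formula resolves the doubt in one direction: the full contents are credited as taken. Because each kit holds 6 tablets more than a week requires, the credit exceeds full compliance for that week (20/14 = 143%). An unreturned kit can therefore never lower a subject's figure; it always raises it, even if nothing in it was taken.

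What is at stake is the compliance summary promised in Protocol Section 9.4.6, for which this is the SAP's only measure. A poorly adherent subject can appear in the band that contains 100%, or appear as an over-user. A reported value above 100% is also ambiguous. With two kits unreturned and the other weeks perfect, 117.1% is consistent with true intake of 60% (none taken from them), 100% (14 taken from each) or 117.1% (all 40 taken), and no table in SAP Section 10.2 separates the three.

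**Working it through.** **Inputs**
- Tablets per kit: 20 (Protocol 5.1.1).
- Dose: 2 tablets per day, so 14 per 7-day week (Protocol 5.1.3).
- Dispensing in Stage 1: Weeks 0, 1, 2, 3 and 4, so 5 times (Protocol Table 2). One kit per visit is an assumption, inferred from the 7 + 3 day kit.
- Dosing span: 35 days, an assumption matching the 5-week stage. Expected tablets: 35 × 2 = 70.

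**The plan's own figure.** The documents give no worked compliance percentage. The related figure is days per kit: 20 / 2 = 10 days, or 14 tablets needed plus 6 extra. This agrees with Protocol 5.1.1.

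**Formula under SAP 10.2.** Compliance = 100 × (dispensed − returned) / (days × 2).

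**Perfect subject.** 5 × 20 = 100 dispensed, 5 × 6 = 30 returned: (100 − 30)/70 = 100%. The formula works when all leftovers come back.

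**k kits unreturned and untaken, the others used as planned.** Returned = 6(5 − k).
- Reported = [100 − 6(5 − k)]/70 = (70 + 6k)/70
- True = 14(5 − k)/70

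| k | Reported | True | Reported band | True band |
|---|---|---|---|---|
| 1 | 76/70 = 108.6% | 56/70 = 80.0% | 80 to 120% | 80 to 120% |
| 2 | 82/70 = 117.1% | 42/70 = 60.0% | 80 to 120% | 60 to <80% |
| 3 | 88/70 = 125.7% | 28/70 = 40.0% | >120% | 40 to <60% |

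Each such kit adds 6/70 = 8.6 points to the reported value and removes 14/70 = 20 points from the true one.

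**Sensitivity of the two-kit case**
- Dosing span of 32 to 38 days: 82/64 = 128.1% down to 82/76 = 107.9%. At 34 days it is 82/68 = 120.6%, so placement in the 80 to 120% band needs a span of at least 35 days.
- One of the two is the last kit, last dose on day 28: 82/56 = 146.4%, true 42/56 = 75%.
- Both are the last kits, last dose on day 21: 82/42 = 195.2%, true 42/42 = 100%.
- The three returned cards are empty: 100/70 = 142.9%, true 60/70 = 85.7%.
- Over 10 weeks, four of ten kits unreturned and untaken: (200 − 36)/140 = 117.1%.

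The size varies, but the reported value is above the true one in every case.

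**Dropping the affected weeks instead.** Removing the two unreturned weeks from numerator and denominator gives 42/42 = 100% for a subject whose true intake is 60%. That does not correct the error.

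**The case against.** The strongest reply is that little depends on this number. Compliance is only summarized. The primary analysis runs on the full analysis sets, which are defined by randomization, at least one dose and HAMD-17 data (SAP 4 and 12). This stands, and it rules out any claim that the efficacy result is affected.

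A reader might infer more on four points, and the documents do not support it.

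- *That the per-protocol sets would keep non-adherent subjects.* SAP Section 4 bases those sets on deviations with substantial impact on the primary outcome, with precise reasons to be fixed before lock. No compliance threshold is stated. The risk is conditional. It is not negligible, since a per-protocol analysis is one of two sensitivity analyses for HAMD-17 (SAP 13.1.2) and the only one named for SDS (SAP 13.2).
- *That the formula lets subjects past the missed-dose discontinuation rule.* Protocol Section 5.1.5 counts missed doses and does not use this percentage. Accountability is checked at each weekly visit. The two-kit subject misses 14 daily doses and meets that rule if the site detects it.
- *That lost kits cannot be told from overdoses.* Intake of "any amount more than the prescribed 2 tablets in a given day" goes on a separate Overdose form within 24 hours, and overdoses are also captured as deviations (Protocol 5.1.6). A returned empty card and a missing one should differ in site records. Plasma levels offer a further check, though not for placebo subjects, who are 141/188 = 75% of Stage 1. The ambiguity lies in the compliance table, not in everything the trial collects.
- *That 80 to 120% is a declared acceptable range.* The SAP only lists tabulation levels. Splitting the band at 100% would be a preference and is not needed here.

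It is also fair to say that, of the one-, two- and three-kit cases, only the two-kit one moves silently from a lower band into 80 to 120%. An unreturned kit that was in fact used as planned costs only 8.6 points. How often kits go unreturned is not given. These points limit the size of the problem. They do not make the formula right, because it raises compliance for drug that was not taken.

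**Conclusion.** The point holds as a defect in a stated derivation, with limited reach. Under SAP 10.2 each unreturned, untaken kit raises reported Stage 1 compliance by 8.6 points while true intake falls by 20, so the error has the wrong sign. The two-kit subject is placed in too high a band and the three-kit subject is labelled an over-user; the one-kit subject is overstated by 28.6 points (108.6 − 80.0) without changing band.

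These figures rest on one kit per weekly visit, a 35-day dosing span, nothing taken from the unreturned kits and all other weeks as planned. The direction does not depend on those exact values. The number of subjects affected is unknown. The consequence is a misleading descriptive table, with an effect on the per-protocol sets only if compliance becomes an exclusion reason before lock, and none on the primary analysis.

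**What to change.** In SAP Section 10.2:

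1. State that tablets in a kit or card that was not returned are not counted as taken.
2. Report, by treatment group and stage, the number of subjects with unreturned drug and the number of kits involved.
3. For those subjects, present compliance as two bounds over the full dosing period, keeping the denominator at days × 2. The lower bound takes 0 tablets from the unreturned kits; the upper takes 2 per day for the days they covered. In the two-kit example these are 42/70 = 60% and (42 + 28)/70 = 100%. Do not drop the affected interval, since that reports 100% alone.
4. Before lock, check each value above 100% against accountability records and Overdose forms.

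If compliance is later chosen as a per-protocol exclusion reason, the same document should say which bound applies.

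The cost is a short SAP change and a little more programming. Accountability is already scheduled at every visit, but whether returns are captured kit by kit on the eCRF cannot be seen from the documents and should be confirmed. The downside is a range instead of a single value for affected subjects.

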11. PRIOR AND CONCOMITANT MEDICATION

Prior medication is defined as any medication with the start and stop dates prior to the date of the first dose of study drug. Concomitant medication is defined as any medication with a start date prior to the date of the first dose of study drug and continuing past the first dose of study drug or with a start date between the dates of the first and last doses of study drug, inclusive. Any medication with a start date after the date of the last dose of study drug will be considered as post-treatment medication. Medications will be coded using WHO Drug Dictionary March 2016 or newer version.

Concomitant medication will be assigned to 2 stages for the summary of concomitant medication by stage. A concomitant medication may be assigned to both Stage 1 and Stage 2.

The concomitant medication will be assigned to Stage 1 if the start date of any concomitant medication is prior to or on the Stage 2 randomization date (or the Study Week 5 visit date for those who were not randomized into Stage 2).

The concomitant medication will be assigned to Stage 2 if the stop date of any concomitant medication is on or after the Stage 2 randomization date (or the Study Week 5 visit date for those who were not randomized into Stage 2).

Please refer to Section 5.5 for the imputation of missing or incomplete medication start or stop dates. In general, if missing or incomplete dates make the determination impossible, the medication will be considered as concomitant and the concomitant medication will be assigned to both Stage 1 and Stage 2.

Psychiatric Medication History

The number and percentage of subjects taking psychiatric medications collected on the Psychiatric Medication History CRF pages will be tabulated by Anatomical/Therapeutic/Chemical (ATC) Level 3, preferred term, treatment group, and overall for SAS1 and SAS2 separately. Multiple medication usage by a subject in the same category will be counted only once. Listing of all psychiatric medications will be provided.

Prior and Concomitant Medications

Prior and concomitant medications will be summarized separately. The number and percentage of subjects will be tabulated by ATC Level 3, preferred term, treatment group, and overall for SAS1 (up to Study Week 5 for concomitant medications) and SAS2 (from Study Week 5 to Study Week 10 for concomitant medications) separately. Multiple medication usage by a subject in the same category will be counted only once. Listing of all prior and concomitant medications will be provided.

Statistical Analysis Plan
2018

21 August

Concomitant medications and the incidences will also be summarized for SAS1 over 10 weeks of the study by ATC Level 3, preferred term, and treatment group. The concomitant medication incidence is determined with the number of subjects exposed to a treatment (placebo vs. pimavanserin) who took a concomitant medication while on that treatment divided by the total number of subjects exposed to that treatment.

Post-Treatment Medications

Post-treatment medications will be summarized for SAS1 by ATC Level 3, preferred term, and the study drug (placebo vs. pimavanserin) of which subjects received their last doses.

12. EFFICACY ANALYSES

All efficacy analyses will be performed using the planned treatment assignments for FAS1 and FAS2. Sensitivity analyses of the primary and key secondary efficacy endpoints will be performed using the planned treatment assignments for PAS1 and PAS2.

For Stage 1, Baseline is Study Week 0 and Week 5 is Study Week 5. For Stage 2, Baseline is Study Week 5 and Week 5 is Study Week 10.

Summary statistics for all the efficacy endpoints will be provided by visit and treatment group for FAS1 in Stage 1 (5 weeks), FAS2 in Stage 2 (5 weeks), and the subjects in FAS1 who were not randomized to the pimavanserin group in Stage 2 (10 weeks). Summary statistics for all the efficacy endpoints will also be provided by treatment group in Stage 2 for FAS2 from Baseline (Study Week 0) to Study Week 5.

12.1 Efficacy Endpoints

Primary Efficacy Endpoint

The primary efficacy endpoint is the change from Baseline to Week 5 in the HAM-D-17 total score.

Key Secondary Efficacy Endpoint

The key secondary efficacy endpoint is the change from Baseline to Week 5 in the SDS mean score.

Other Secondary Efficacy Endpoints

Other secondary efficacy endpoints are the following:

- Treatment response and remission rates at the end of 5-week treatment period
- Change from Baseline to Week 5 in CGI-S score
- CGI-I score at Week 5
- Change from Baseline to Week 5 in SF-12 score
- Change from Baseline to Week 5 in DAI-10 score
- Change from Baseline to Week 5 in KSS score

- Change from Baseline to Week 5 in MGH-SFI score
- Change from Baseline to Week 5 in BIS-11 score
- Change from Baseline to Week 5 in SIS score

Treatment response is defined as a reduction from Baseline in HAMD-17 total score of 50% or more. Remission is defined as a HAMD-17 total score less than or equal to 7.

